[Relationship]	Integrate into the date of the “related” event.
[Outcome (outcome confirmation date)]	The same year: Death>Not recovered>Recovered with sequela>Unknown>Recovering>Recovered>Not provided Different years: Integrate into the final year.
	Of note, when the onset date is unknown or not provided, the event with the onset date should be selected.
	<Processing order> Process [1]: Events which occurred in the same year and on the same date Process [2]: Events which occurred in different years but on the same date Process [3] Events which occurred in the same year but on different dates Process [4] Events which occurred in different years and on different dates.
Test	Exclude “unknown”, “not provided” and “not assessable” from test. Do not conduct a test for the items with multiple answers. When χ^2 test is conducted and the degree of freedom (DF) is 1, conduct Fisher’s exact test as well for the item.

<Handling of items>

Number of sites for the survey	Department codes (per contract) are included in the DCF site code. Count the number of site as one.
Primary disease	Give priority to "1=HIV Infection" throughout a year. "AIDS" should be regarded as "HIV Infection" in "2. Others". Others should be "Others". [Stratification] HIV Infection, Others
Sex	Use the value in the CRF at the first administration of CELSENTRI Tablets. [Stratification] Men, Women
Presence/absence of pregnancy	Patients who receive CELSENTRI Tablets for at least one day during pregnancy (if the date of last menstrual period (LMP) is unknown after LMP, see Week 0 of pregnancy or later; if both are unknown, see the pregnancy diagnosis date or later) among the patients in "Sex:3" (Pregnancy: present). Include the cases with "Women" in "Sex". [Stratification] Absence, Presence, Unknown/not provided

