Complications	Use the complications provided in the CRF at the first administration of CELSENTRI Tablets. The events that occurred and did not recover before the first administration of CELSENTRI Tablets in the 'adverse event' column. [Stratification] Absence, Presence, Unknown/not provided
Type of complications	Complications provided in the CRF at the first administration of CELSENTRI Tablets <Multiple-answers are acceptable in this column> In addition, reflect the ViiV Healthcare K.K.'s instruction for data amendment. [Stratification] • "Haemophilia": complications are present "1. Haemophilia"

	
•"Liver disorder": the disease selected as liver disorder in 'complication is present': 3. Hepatitis A", "4. Hepatitis B", "5. Hepatitis C", "6. Other liver disorders", or "8. Others"

The mean daily dose	
The mean dose for "administration period" Even if "administration period" is unknown, the provided value should be regarded as the mean when there is no change in "the dose". [Stratification] >minimum and < 2 tablets, 2 tablets, >2 tablets and <maximum, unknown/not provided

Dosing frequency	
Calculate the number of dosing in a day. [Stratification] 1, 2, ≥3 and ≤maximum, unknown/not provided

Administration period	
\sum (final administration date - first administration date+1). Exclude the washout period. [Stratification] ≤180 days, >180 and ≤365 日、 >365 and ≤730 日、 >730, unknown/not provided

Administration period <cumulative>	
Count "the number of patients" by accumulating "administration period", count "the number of patients with adverse reactions" based on the "administration period" until the first adverse reaction occurred, and count "the number of adverse reactions" based on the "administration period" until the applicable adverse reaction occurred. Exclude the washout period. [Stratification] ≤180 days, >180 and ≤365 日、 >365 and ≤730 日、 >730, unknown/not provided

Total dose	
\sum {(Final administration date - First administration date+1) × a daily dose}. Exclude the washout period.[Stratification]≤360 tablets, >360 tablets and ≤730 tablets, >730 tablets and ≤1460 tablets, >1460 tablets, unknown/not provided

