Total dose <cumulative>	
Count "the number of patients" by accumulating "total dose", count "the number of patients with adverse reactions" based on the "total dose" until the first adverse reaction occurred, and count "the number of adverse reactions" based on the "total dose" until the applicable adverse reaction occurred. Exclude the washout period. [Stratification] ≤360 tablets, >360 tablets and ≤730 tablets, >730 tablets and ≤1460 tablets, >1460 tablets, unknown/not provided

Continued/discontinued	
Display 'continued/suspended' of the final administration period throughout a year. [Stratification] Continued, Suspended, Unknown/not provided

Presence/absence of concomitant drugs	
If there is a drug concomitantly used in the "administration period" of CELSENTRI Tablets, select "2=present". If there is a drug concomitantly used at least for a day, select "2=present". Of note, if only one date is overlapped when two anti-HIV drugs are used on the same day (as the first administration for one and the final administration for the other), it should be regarded as "replacement" and not handled as a concomitant drug. [Stratification] Absence, Presence, Unknown/not provided

Number of concomitant drugs	
Number of types of concomitant drugs used in the "administration period" of CELSENTRI Tablets Drugs concomitantly used at least for a day. Of note, if only one date is overlapped when two anti-HIV drugs are used on the same day (as the first administration for one and the final administration for the other), it should be regarded as "replacement" and not counted as a concomitant drug. [Stratification] ≤2 drugs, ≥3 and ≤5 drugs, ≥6 drugs

Type of concomitant drugs	
Count the breakdowns of designated concomitant drugs. Of note, when a patient used multiple drugs in the same classification, count the drugs as one. <Multiple-answers are acceptable in this column> [Stratification] Anti-HIV drug, Other anti-virus drugs, Others

Number of concomitantly-used anti-HIV drugs	Number of types of anti-HIV drugs used in the “administration period” of CELSENTRI Tablets Drugs concomitantly used at least for a day. Of note, if only one date is overlapped when two anti-HIV drugs are used on the same day (as the first administration for one and the final administration for the other), it should be regarded as “replacement” and not counted as a concomitant drug. [Stratification] a single-use drug, 1 drug, 2 drugs, 3 drugs, ≥4 drugs

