*A list of adverse reactions per patient background, etc.	Prepare a list for adverse reactions in <General Definitions>. © Displayed items: No., patient registration number, age, pediatrics, the elderly, race, presence/absence of pregnancy, presence/absence of complications, haemophilia, renal disorder, hepatitis A, hepatitis B, hepatitis C, others, liver disorder, syphilis, others, presence/absence of haemophilia, presence/absence of liver disorder, presence/absence of renal disorder, name of complication, presence/absence of allergy, presence/absence of concomitant treatment, name of concomitant treatment, presence/absence of concomitant drugs, number of concomitant drugs, presence/absence of concomitant anti-HIV drugs, number of concomitant anti-HIV drugs, administration period, long-term administration, presence/absence of adverse events, presence/absence of adverse reactions, name of adverse reactions (PT), seriousness, outcome, days to the onset, relationship with CELSENTRI
Incidence of adverse reactions per patient background	Prepare a table of incidence of adverse reactions on the following patient-background items: Follow the above <<Handling of Items>> for the definitions of each item per background. © Displayed items: primary disease, sex, presence/absence of pregnancy, age, inpatient/outpatient classification, treatment history of HIV infection, race, route of transmission, duration of disease, medical history, allergy, complication, type of complication, renal disorder, liver disorder, the mean daily dose, administration period, administration period [cumulative], total dose, total dose [cumulative], continued/discontinued, concomitant drug, number of concomitant drugs, type of concomitant drugs, number of concomitant anti-HIV drugs, type of concomitant anti-HIV drugs, presence/absence of CYP3A inducer, presence/absence of haemophilia, haemophilia AB, CDC classification of severity prior to administration, tropism classification at the first administration, concomitant treatment, blood coagulation factor (all cases and the cases with haemophilia) Calculate the minimum and the maximum for age, duration of disease, the mean daily dose, administration period, total dose while calculate the

	mean and the standard deviation for age as well (Of note, as to the description age for example, calculate the age of a patient in his 30s will be calculated as 30 years old).

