Data on the incidence of adverse reactions per patient background	Display the incidence of adverse reactions per patient background for each patient.
A list of the onset status of adverse reactions/infections per patient background	Prepare a list of the onset status of adverse reactions/infections for each patient background item below. Follow ‘adverse reactions’ of <General Definitions> for the onset status of adverse reactions while follow the above <Handling of Items> for the definition of each patient-background item. © Displayed items: primary disease, sex, presence/absence of pregnancy, age, inpatient/outpatient classification, treatment history of HIV infection, race, route of transmission, duration of disease, medical history, allergy, complication, type of complication, renal disorder, liver disorder, the mean daily dose, administration period, administration period [cumulative], total dose, total dose [cumulative], continued/discontinued, concomitant drug, number of concomitant drugs, type of concomitant drugs, number of concomitant anti-HIV drugs, type of concomitant anti-HIV drugs, presence/absence of haemophilia, haemophilia AB, CDC classification of severity prior to administration, concomitant treatment, blood coagulation factor (all cases and the cases with haemophilia)
Number of days to administer until the day on which adverse reactions first occurred	Prepare a table by number of days ≤ 180 days, 180 days < ≤ 365 days, 365 days < ≤ 730 days, 730 days <
The incidence of adverse reactions per concomitant drug	Prepare a table of incidence of adverse reactions regarding concomitant drugs per drug code (the first 7 digits). Follow “Co-administration” of <General Definitions> for the definition of co-administration.
A table of patient numbers per concomitant drug	Prepare the patient registration numbers for each drug code (the first 7 digits) regarding concomitant drugs with and without patients with adverse reactions. Follow “Co-administration” of <General Definitions> for the definition of co-administration.
The incidence of adverse reactions per complication	Prepare a table of incidence of adverse reactions per PT regarding complications and other contents. The definition of complications is applied to the patients with “complications” of <Definitions of Items>.

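### Adverse-reaction incidence by final administration period and final total dose mixes observation time and stopping at the reaction with any real effect, so it cannot be read as a duration or dose effect

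*SAP*

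**What the plan says.** SAP, Handling of items, defines the administration period as a sum of "final administration date - first administration date+1). Exclude the washout period". Total dose uses the same days multiplied by the daily dose: "Final administration date - First administration date+1) × a daily dose". Both apply to every patient, with or without a reaction, and neither stops at the reaction.

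The same section defines a cumulative version of each, which places reactors by exposure up to onset. For the period the instruction is: "count 'the number of patients with adverse reactions' based on the 'administration period' until the first adverse reaction occurred". For total dose it is: "count 'the number of patients with adverse reactions' based on the 'total dose' until the first adverse reaction occurred".

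SAP part 3, *Incidence of adverse reactions per patient background*, lists all four together ("administration period, administration period [cumulative], total dose, total dose [cumulative], continued/discontinued"), and the onset-status list that follows repeats them. Protocol 8.2(1) says that factors affecting the onset of ADRs will be examined when incidence is tabulated by factor. The SAP does not adjust the non-cumulative rows for time at risk and does not say how to read them.

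The period is cut at 180, 365 and 730 days, as in the separate table of days to first reaction ("≤ 180 days, 180 days < ≤ 365 days, 365 days < ≤ 730 days, 730 days <"). Total dose is cut at 360, 730 and 1460 tablets.

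**The concern.** A background factor should be fixed before the outcome. Final exposure is not, for two reasons.

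- **Observation time.** A patient treated for years had years in which to react. Even at a constant hazard, a larger share of long-treated patients will have reacted, so the gradient rises.
- **Stopping at the reaction.** A patient who stops early because of a reaction is held in a low stratum by that reaction. This loads reactors into the short strata, so the gradient falls.

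The balance depends on how many reactors stop and how long the others stay. Neither is a property of dose or duration. Someone looking for factors affecting onset could see a duration or cumulative-dose trend where none exists, or miss a real one. Identifying factors that affect safety is a stated objective (Protocol section 1).

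**Working it through.** The plan states no event rate, total sample size or significance level on this point, so there is no figure to reproduce.

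**Inputs from the documents.** The definitions and cut-points above. Enrollment from 1 April 2009 to 31 March 2017 (Protocol section 6) and data lock on 26 March 2018 (SAP, Handling of cases) imply roughly 360 to 3281 days from entry to lock.

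**Assumptions.** First dose to lock uniform over 360–3280 days. Annual reaction risk 5% or 10%, constant, with no effect of dose or duration. Other discontinuation 0.2 or 0.5 per year. Share of reactors who stop at the reaction from 0 to 100%. 2 tablets/day. 400,000 simulated patients per setting.

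**1. Cut-points.** 2 × 180 = 360; 2 × 365 = 730; 2 × 730 = 1460. For a patient on 2 tablets/day throughout, the total-dose row repeats the period row.

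**2. Non-cumulative row, no true effect** (% with a reaction, by final days on drug):

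| Annual risk | Other discontinuation | Reactors stopping | ≤180 | 181–365 | 366–730 | >730 |
|---|---|---|---|---|---|---|
| 5% | 0.2/yr | none | 1.3 | 3.7 | 7.3 | 19.6 |
| 5% | 0.2/yr | half | 11.7 | 12.5 | 10.4 | 15.5 |
| 5% | 0.2/yr | all | 20.3 | 20.2 | 13.5 | 10.8 |
| 5% | 0.5/yr | none | 1.3 | 3.7 | 7.0 | 16.0 |
| 5% | 0.5/yr | all | 9.1 | 9.1 | 7.5 | 6.9 |
| 10% | 0.2/yr | none | 2.6 | 7.4 | 14.3 | 35.4 |
| 10% | 0.2/yr | all | 35.0 | 34.2 | 24.2 | 20.3 |

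Hand check of the 5%, 0.2/yr rows. The hazard is −ln(0.95) = 0.0513 per year.

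- *No stopping:* incidence at final time T is 1 − exp(−0.0513 × T/365). At the interval midpoints of 90, 272.5 and 547.5 days this gives 1.3%, 3.8% and 7.4%.
- *All stopping:* before lock can intervene (≤180 days), treatment ends by reaction or by other discontinuation, so the reactor share is 0.0513 / (0.0513 + 0.2) = 20.4%. In later strata, patients still on drug at lock dilute it.

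Setting the hazard at exactly 0.05 gives about 1.2% to 19% and 20% to 11%.

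**3. With a true dose effect.** Half on 2 and half on 4 tablets/day, purely for illustration; hazard ratio 3; 5% annual risk at 2 tablets; other discontinuation 0.3 per year. From lowest to highest stratum, the total-dose row runs from 1.4% to 28.8% if nobody stops (1.0% to 15.8% with no dose effect). If all stop, it *falls* from 22.3% to 18.3%. The mean-daily-dose row shows the effect either way, at about 11% against 28%.

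**4. Cumulative row, no true effect** (5%, 0.2/yr). I read it as first reactions in the stratum divided by patients reaching it, since the SAP does not spell out the denominator. It gives 2.4 / 2.4 / 4.0 / 9.8% with no stopping and 2.4 / 2.5 / 4.3 / 10.8% with all stopping. It rises because the strata have unequal widths and the last is open-ended.

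**5. Person-time rate, same data.** First reactions per person-year at risk in each interval are 0.051–0.052 in all four strata, whatever share stops.

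**The case against.** The strongest reply is that these are descriptive background rows in an exploratory survey, and that the SAP already supplies better views: cumulative rows alongside, a separate mean-daily-dose row, a table of days to first reaction, and days to onset in the listings. The SAP never calls the rows a dose-response analysis. This stands as mitigation and makes a hidden signal less likely, but none of it corrects or explains the rows themselves.

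The sizes rest on assumptions, and so does the reversal. With treatment length exponential (mean 3 years, capped at 8) and a 10% per year hazard, the all-stop row is nearly flat at 23.0 / 23.1 / 23.1 / 21.4%. With no stopping, the same model rises from 2.3% to 35.6%. The gradient still depends on stopping, but a fall is not inevitable.

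Three stronger readings are tempting and not supported:

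- *The rows are tested.* A reader might infer this from the general Test entry, but that entry is conditional ("When χ^2 test is conducted and the degree of freedom (DF) is 1, conduct Fisher’s exact test as well for the item") and lists no items. If they were tested at an assumed 0.05 with 5% annual risk and other discontinuation of 0.3 per year, chi-square would reject under no effect in 73%, 11% and 14% of samples of 200 for none, half and all stopping. That is a consequence of testing, not evidence that testing is planned.
- *The rows carry no dose information.* Step 3 shows that they respond to dose. The response cannot be separated from the artefacts.
- *The total-dose row always duplicates the period row.* That holds only at a constant 2 tablets/day. The SAP provides mean-dose strata below and above 2, and no document gives the split.

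**Conclusion.** The concern holds as a limit on interpretation. As defined, the non-cumulative period and total-dose rows cannot be read as effects on ADRs. With no true effect, the gradient at 5% annual risk and 0.2 per year other discontinuation goes from a fifteenfold rise (19.6 / 1.3 ≈ 15) to a near-halving (10.8 / 20.3 ≈ 0.53) on the assumed stopping share alone. The definitions come from the SAP; reaction rate, discontinuation, stopping share and dose mix are my assumptions.

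The overall ADR incidence is untouched. What is exposed is the search for factors affecting onset. Simply falling back on the cumulative rows is not enough, because their plain proportions also rise with no effect. The change is worth making: it is cheap and the misleading gradient can be large.

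**What to change.** 1. In SAP part 3, remove the non-cumulative administration-period and total-dose rows from the adverse-reaction incidence table and from the onset-status list. If the regulatory form requires them, print them without a test and with a note that they include exposure after, and curtailed by, the reaction and are not adjusted for time at risk.
2. Keep both rows in the patient composition table in part 2, where they properly describe exposure.
3. For the cumulative rows, divide first reactions in each exposure interval by the person-time at risk in it, counting each patient until first reaction or end of treatment and excluding washout as the SAP already does. For total dose, count the time during which accumulated dose lies in the stratum. State the denominator explicitly.

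The cost is SAP wording and slightly more programming from dates already collected. The downside is that a required form may keep the rows as untested description. Person-time rates also have a limit: a falling rate over time can still reflect susceptible patients reacting or leaving early.

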8.2 Analysis Methods

(1) Analyses related to safety evaluation

In the safety analysis set, the primary analysis items will be the occurrence of common ADRs and the incidence of ADRs (proportion of patients with AEs with which Celsentri's causal

relationship could not be denied). In addition, when tabulating the incidence of ADRs by factor such as patient background characteristics, factors affecting the onset of ADRs will be also examined.

(2) Analyses related to efficacy evaluation

Efficacy parameters for anti-HIV drugs such as a CD4 count, number of HIV-RNA copies and CDC classification will be tabulated and analyzed by patient background characteristic to examine factors affecting the efficacy of Celsentri. In patients tested for tropism, the relationship with the status of tropism change will be also evaluated.

9. Organization System for the Implementation of the Survey

The survey will be conducted using the system described in Appendix 3 in accordance with the procedures for the implementation of the HRD cooperative investigation (Appendix 2). The procedures for notifying ADRs, etc. are presented in Appendix 4.

This survey will be performed as a cooperative investigation by companies marketing drugs for the treatment of HIV infection^{Note 1)} using a common CRF. The common CRF for the drug use-results survey may be completed one copy for one patient even if a few anti-HIV infection drugs are coadministered during the reexamination period.

10. Name and Address of the Contractee, and the Scope of the Concerned Outsourced Activities

(1) Contractee

Address: PPD [redacted]

Name: PPD [redacted], PPD [redacted] CMIC PMS Co., Ltd.

Name of the person responsible for implementation: PPD [redacted], Postmarketing Surveillance Operation Implementation Supervisor

(2) Scope of outsource activities

- 1) Request to and contract with institutions
- 2) Issuance of a user's ID and password to each investigator
- 3) Retention of the originals of enrollment forms
- 4) Sending the copies of enrollment forms
- 5) Verification of registration and investigation items entered and sent by the investigators
- 6) Collection of the originals of CRFs
- 7) Preparation and collection of the statement of confirmation
- 8) Sending the copies of CRFs
- 9) Arranging reinvestigation items
- 10) Request for a reinvestigation
- 11) Retention of the originals of CRFs
- 12) Sending the CRFs (final version)
- 13) Data locking
- 14) Coding
- 15) Data tabulation/analyses

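### Final continued/discontinued status is listed as a background factor for adverse-reaction incidence, though a reaction can cause it; the row can mislead in either direction and should not be tested or read as a factor.

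*SAP*

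**What the plan says.** In the SAP, section 3) (tables for the safety analysis group), the entry on incidence of adverse reactions per patient background reads: "Prepare a table of incidence of adverse reactions on the following patient-background items". The items that follow include "total dose [cumulative], continued/discontinued, concomitant drug, number of concomitant drugs". The list of onset status of adverse reactions/infections, in the same section, also names continued/discontinued.

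SAP Handling of items defines the row as the status "of the final administration period throughout a year", with the levels "Stratification] Continued, Suspended, Unknown/not provided". Sex, race and inpatient/outpatient classification, by contrast, use the case report form at first administration.

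The Test rule in the SAP General Definitions drops unknown, not provided "and “not assessable” from test". Its only exemption for whole items is: "Do not conduct a test for the items with multiple answers". Where a chi-square test is done with one degree of freedom, Fisher's exact test is added.

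Protocol 8.2(1) gives the use of the breakdown by factor: "factors affecting the onset of ADRs will be also examined".

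**The concern.** A factor affecting the onset of a reaction has to be in place before the reaction. Status in the last administration period is known only at the end of observed treatment. If some patients stop because of a reaction, they move into the suspended group and raise its incidence, even when every patient had the same risk at the start. The row then shows the effect of reactions on stopping, displayed as if it were the effect of a patient characteristic on reactions.

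A second distortion works the other way. Patients who continue are on drug longer and have more time in which to have a reaction.

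The row stands among true baseline items with nothing to mark the difference. Protocol section 1 names factors likely to affect safety among the matters used to judge whether a further survey or study is needed. A spurious difference here, or a true null produced by two cancelling distortions, could be misread in that judgement.

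**Working it through.** **There is no plan figure to reproduce.** The documents state no sample size, significance level, reaction rate or stopping rate for this point. All rates, the sample sizes and the two-sided 0.05 level below are assumptions.

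**1. Is the row tested?** It is a single-answer item. Once unknown/not provided is dropped, two levels remain, so there is one degree of freedom. The multiple-answer exemption does not apply. Chi-square plus Fisher follows on a plain reading of the general rule. The table entry itself orders no test, and the mock-up is not available.

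**2. Is the row tied to the time of onset?** No. SAP Handling of items counts the cumulative administration period and cumulative total dose up to the reaction. Continued/discontinued has no such anchor, caveat or split by reason. Protocol 7.3 lists the status but no reason for stopping.

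**3. Reverse causation alone.** Every patient has reaction risk p, the background stopping probability is s0, and a reaction causes stopping with probability q.
- P(stop | reaction) = 1 − (1 − s0)(1 − q)
- P(stop) = p·P(stop | reaction) + (1 − p)·s0
- Incidence in suspended = p·P(stop | reaction) / P(stop)
- Incidence in continued = p·[1 − P(stop | reaction)] / [1 − P(stop)]

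With p = 0.10 and s0 = 0.30:
- q = 0: 10.0% against 10.0%.
- q = 0.25: P(stop | reaction) = 0.475 and P(stop) = 0.3175. Suspended 0.0475/0.3175 = 15.0%; continued 0.0525/0.6825 = 7.7%.
- q = 0.5: P(stop | reaction) = 0.65 and P(stop) = 0.335. Suspended 0.065/0.335 = 19.4%; continued 0.035/0.665 = 5.3%.

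Share of 2,000 simulated surveys with p < 0.05 (chi-square / Fisher):

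| N | q = 0 | q = 0.25 | q = 0.5 |
|---|---|---|---|
| 100 | 3.8% / 2.2% | 21.9% / 16.6% | 58.3% / 50.8% |
| 200 | 4.8% / 3.6% | 38.5% / 33.4% | 86.6% / 84.4% |
| 400 | 5.2% / 4.5% | 59.8% / 55.5% | 98.6% / 98.4% |

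Over N = 100 to 400, p = 10% to 20% and s0 = 30% to 50%, chi-square rejection runs from 12% to 85% for q = 0.25 and from 32% to 100% for q = 0.5.

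**4. Sensitivity to the stopping contrast.** Take 15% incidence and set the stopping shares directly. Power ≈ Φ[(d − 1.96·SE0)/SE1], where d is the difference in incidence, SE0 the pooled and SE1 the unpooled standard error.
- Stopping 60% with a reaction, 30% without: suspended 0.09/(0.09 + 0.255) = 26.1%; continued 0.06/(0.06 + 0.595) = 9.2%. At N = 200 the groups are 69 and 131, d = 0.169, SE0 = 0.0531, SE1 = 0.0586, so power is Φ(1.11) ≈ 0.87. At N = 300 it is 0.96.
- Stopping 40% against 30%: suspended 0.06/(0.06 + 0.255) = 19.0%; continued 0.09/(0.09 + 0.595) = 13.1%. At N = 200 the groups are 63 and 137, d = 0.059, SE0 = 0.0544, SE1 = 0.0573, so power is Φ(−0.83) ≈ 0.20. At N = 300 it is about 0.28, and at N = 500 about 0.41.

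**5. Adding exposure time.** Constant hazards by simulation: reaction 0.05 per year, stopping for other reasons 0.1 or 0.3 per year, follow-up uniform over 0 to 8 years (the enrollment period in Protocol section 6 spans 8 years). Incidence, suspended against continued:

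| q | other stopping 0.1/year | other stopping 0.3/year |
|---|---|---|
| 0 | 10.7% vs 15.4% | 8.3% vs 11.5% |
| 0.25 | 17.6% vs 12.0% | 9.8% vs 8.9% |
| 0.5 | 23.7% vs 8.3% | 11.4% vs 6.1% |

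With the same reaction hazard for everyone, the row can favour either group or look nearly level.

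**The case against.** **Testing is inferred.** The Test rule names no table, its wording on chi-square is conditional, and the mock-up might show no p-value on this row. This stands as a limit on the claim. It does not rescue the row, because the split in incidence misleads even without a p-value.

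**The protocol does not call this row a factor.** Protocol 8.2(1) speaks of factors in general and does not name continued/discontinued. The examples in Protocol section 11(2) of what would prompt a further study do not include a subgroup difference. That is true and limits the consequences. But the SAP places the row among the background items of the table that carries out 8.2(1), with nothing to set it apart.

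**The link from reaction to stopping may be weak.** The documents do not say how often reactions lead to stopping. Because only the last period counts, a patient who interrupted and later resumed is classed as continued. This also stands.

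**The stronger reading.** A reader might infer that the row is bound to show a large, significant, false risk factor. The documents do not support that. They give none of the rates needed. In the milder case of step 4 the test would usually not be significant, and step 5 shows that the direction itself can change.

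**Conclusion.** The point holds as a structural one: final continued/discontinued status is set after baseline and may result from the reaction, so neither a difference in this row nor the lack of one says anything about factors affecting onset. The row is liable to show a spurious association in either direction. This part rests on the SAP's own definition and needs no assumed rate.

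The size is open. Under the assumptions above, with no true risk factor, the row ranges from 23.7% against 8.3% (higher in suspended), through nearly level, to 10.7% against 15.4% (higher in continued). The chance of a significant test ranges from about the nominal level to near certainty.

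The reach is limited to this row of the incidence table and the same item in the onset-status list. The overall incidence of adverse reactions and the occurrence of common reactions, the primary items in Protocol 8.2(1), are not affected.

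**What to change.** In the SAP, exclude continued/discontinued from the chi-square and Fisher tests and from the examination of factors affecting onset. Then either keep it only in the patient composition table of section 2), or leave it in the incidence table and onset-status list with a note that it is descriptive, untested and not a factor.

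Optionally, report stopping as an outcome: the number and share of patients with an adverse reaction whose final administration date falls on, or within a pre-specified window after, first onset. Two safeguards are needed:
- Describe the result as temporal, not causal, because Protocol 7.3 lists no reason for stopping.
- Show separately the patients whose onset or final administration date was imputed. The Date conversion rule sets an invalid day to 01 for both dates, so an imputed final date can fall before a known onset or tie artificially with an imputed one.

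The cost is SAP wording and, if the option is taken, one derived count from dates already collected. At most one tested descriptive row is lost.
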